9. Disease status: Disease status will be evaluated every 8 weeks by history, physical examination, laboratory studies and bone marrow aspirate and biopsy as indicated by disease state and clinical parameters.
10. Rh- recipients of child bearing potential who are anticipated to receive a Rh+ product will receive Rhogam at standard dose.
11. Anti-coagulant treatment of any form (Heparin/ Warfarin/ Apixaban etc. will be withheld for one day prior to harvesting of cells from the donor
12. IAC products will meet preparation and release criteria as outlined below:
 - a. Donor leukapheresis volume will be 2.5-3.0 blood volumes or as determined by blood services.
 - b. The leukapheresis product will be appropriately labeled with: 2 patient-specific identifiers, the name of the product, the product unit number, the expiration date, donor Rh/ABO type, and the statement: "Caution: New Drug – Limited By Federal Law To Investigational Use Only".
 - c. If there is a major ABO incompatibility, the product will either be split so that no more than 10 ml ABO incompatible RBC be infused/day or undergo RBC depletion to \leq 10 ml of RBC.
 - d. The product will be transported to the [REDACTED] Hospital Transfusion Services where it will undergo irradiation (25 Gy)

according to standard operating procedures. A label indicating irradiation will be attached.

e. The product will then be assigned to the patient and the released product will be transported to and administered to the patient at [REDACTED] after pre-medication of the patient with acetaminophen 650 mg PO and diphenhydramine-HCl 25 mg PO.

d) Preliminary Data

See the research significance section above and references. IAC is an effective therapy for selected patients with renal cell carcinoma. Individual responses have also been seen in AML and CML (6, [name] personal observation). There is also evidence that allogeneic cells can induce a host CD8+ T cell response directed an AML-associated epitope (7).

e) Sample Size Justification/Statistical Analysis

The primary aim of this pilot study is to see if there is acceptable tolerance (no irreversible grade 3 or higher) experimental treatment-related serious adverse effects and any disease response for 10 patients in each cohort. This will ensure that there is at least an 80% chance that the true unacceptable rate is less than 30%. The study will be closed if there is >1 irreversible grade 3 or higher experimental treatment related adverse effect in either cohort.

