If there is (1) a steroid refractory GVHD or (2) graft failure in cohort 2, then the study will stop.

The secondary aim is to determine if there is evidence of disease response to IAC. If there is evidence of disease response in either arm, additional studies will be planned.

f) Study Variables

• *Independent Variables or Interventions*

IAC infusion every 8-12 weeks as tolerated and feasible.

Toxicity will be measured by occurrence of any experimental treatment-related Adverse Events (AE) up to 12 weeks of completion of therapy. The CTCAE Version 4.0 will be utilized for the description and grading of the AE. All symptoms, signs, or diseases assessed as experimental treatment-related will be captured and graded by a study investigator and an attribution will be associated to the experimental therapy (IAC).

Attribution of the AE:

- Definite – The AE is clearly related to the experimental therapy
- Probable – The AE is likely related to the experimental therapy
- Possible – The AE may be related to the study treatment
- Unlikely – The AE is doubtfully related to the study treatment
- Unrelated – The AE is clearly NOT related to the study treatment

Any experimental treatment-related irreversible grade 3 or higher AE (definite, probable or possible) will result in that patient not receiving any further treatment. If the AE corrects completely or to Grade 1 within 2 weeks, repeat treatment as directed by protocol may be utilized. If there is more than one such irreversible experimental treatment-related Grade 3 adverse event, the study will be terminated for that cohort.

Since a major concern is that the IAC might trigger an immune response that results in steroid-refractory GVHD OR graft failure (in cohort 2), specific parameters to diminish the likelihood of these events are included in the inclusion criteria (e.g. durable engraftment and high donor chimerism). Furthermore, the study will be terminated if even a single episode of these events occurs.

Overall response rate will be defined as the proportion of patients meeting the criteria for partial response (PR), very good partial response (VGPR) and complete response (CR). Disease response will be determined by Standards of Blood and Marrow Transplant Program disease-specific parameters.

- *Dependent Variables or Outcome Measures*

Toxicity and disease response will be measured. Disease response will use standard disease-specific parameters.

g) Drugs/Devices/Biologics

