The infusion of irradiated cells may be associated with short-term effects such as fevers, chills, dyspnea and systemic inflammatory symptoms such as shortness of breath due to pneumonia or diarrhea due to colitis. Long-term effects may include infection or autoimmunity. For patients who have received an allogeneic transplant the manifestation of "autoimmunity" might be graft-versus host disease or graft rejection.

(b) Risk Of Imposing An Intervention On Subject With Existing Condition

N/A

(c) Other Foreseeable Risks

The patients receiving therapy with IAC have very high-risk diseases and are receiving IAC as an adjuvant to transplant therapy. It may be hard to determine the toxicity related to their disease, standard treatment (transplant therapy) or the experimental therapy (IAC). In this context all patients will be at risk for infection, bleeding, organ toxicity (including heart, lung, kidney, liver, oropharyngeal, gastrointestinal, neurologic, ophthalmic and bone marrow) some of which might be irreversible and some of which could lead to long-term morbidity and death. These risks are intrinsic to the disease and standard therapy and may be worsened by the experimental therapy.

(d) Observation And Sensitive Information

N/A

(5) Minimizing Risks

The experimental intervention (IAC) involves administration of irradiated Patients receiving IAC will be reviewed weekly at 2 meetings – a weekly transplant meeting and a weekly clinical research meeting. Any SAE considered likely related to IAC will be discussed and presented for biometric evaluation re:stopping rules.

(6) Certificate of Confidentiality

N/A

(7) Potential Benefits to Subjects

IAC may improve clinical outcomes by increasing disease response rates and disease control.

(8) Provisions to Protect the Privacy Interests of Subjects

Patient confidentiality will be strictly maintained according to NIH guidelines.

(a) Research Team Access To Subject Data

The subject's personal health information, identifiers and research data are stored and kept in a secure area in the [REDACTED] computer screens containing personal health identifiers are inaccessible to public view. Only the study doctor and research team will have direct access.

c) Secondary Data – Records/Chart Reviews/Databases/Tissue Banks/etc.

[REDACTED]

20

RESERVED FOR IRB STAMP
DO NOT MODIFY THIS SPACE

Form V

Approval Date:
Expiration Date:

4/23/2021
4/22/2022

N/A

Chart/Record Review Selection

N/A

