The data collected will be stored on clinical trial management software - Oncore in Principal Investigator's computer. All Computers in OHRs are encrypted, password protected and on secured servers. Only the Principal Investigator and/or the research team will have access to the patient's data.

c) Data and Safety Monitoring

Minimal risk is anticipated however there is always the possibility of unanticipated effects. Institutional Data Safety Monitoring Board/ HROC will monitor the data from the research after initial 2-3 patients and based on their suggestions the research will be conducted as is/ Modified or discontinued.

▪ Periodic Data Evaluation

Weekly at the Blood & Marrow Transplantation and Hematologic Malignancies Tumor Study group research meetings.

▪ Type of Data Evaluated

Treatment related toxicities; unanticipated adverse events.

▪ Collection of Safety Information

Patient safety data will be reviewed at both of the above cited weekly meetings.

▪ Frequency Of Data Collection

Weekly. If there is no weekly meeting (e.g. holiday) data will be delayed until the next scheduled meeting.

▪ Reviewer of Data

Principal Investigator reviews all data.

▪ Schedule Of Review Of Cumulative Data

Review of cumulative data will occur weekly at the Hematologic Malignancies Tumor Study Group weekly research meeting.

- **Tests for Safety Data**

Weekly meetings of the Blood & Marrow Transplant Program and Hematologic Malignancies Clinical Research Tumor Study Group review each patient. Experimental treatment-related SAEs will be reported for biometric review.

- **Suspension of Research**

Suspension will take place based upon stopping rules

d) Reporting Results

- **Sharing of Results with Subjects**

Clinical results can only be shared following completion of the study.

- **Individual Results**

Patients will be notified of any abnormal findings or lab results.

- **Aggregate Results**

N/A

- **Professional Reporting**

It is expected that the results of this process will be submitted for publication in a timely manner following the conclusion. [REDACTED] all co-authors prior to submission or use, will review any abstract or manuscript.

- **ClinicalTrials.Gov Registration And Data Reporting**

The study will be registered in accordance to applicable institutional guidelines.

7) Data and/or Specimen Banking

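### Adverse events are to be captured once judged IAC-related, which conflicts with the plan's own attribution scale and can leave events out of the primary toxicity dataset

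*Combined protocol and SAP*

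**What the plan says.** Toxicity is the primary objective. Section e) Sample Size Justification/Statistical Analysis looks for acceptable tolerance and "any disease response for 10 patients in each cohort". It claims: "This will ensure that there is at least an 80% chance that the true unacceptable rate is less than 30" (percent). It sets the limit: "The study will be closed if there is >1 irreversible grade 3 or higher experimental treatment related adverse effect in either cohort".

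Section f) Study Variables defines the endpoint: "Toxicity will be measured by occurrence of any experimental treatment-related Adverse Events (AE) up to 12 weeks of completion of therapy". It then gives the capture rule: "All symptoms, signs, or diseases assessed as experimental treatment-related will be captured and graded by a study investigator". The attribution scale that follows has five grades and ends with: "Unrelated – The AE is clearly NOT related to the study treatment". For the irreversible grade 3 or higher rule, definite, probable and possible events count as related.

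Under Risks to Subjects, item (4)(c) Other Foreseeable Risks says: "It may be hard to determine the toxicity related to their disease, standard treatment (transplant therapy) or the experimental therapy (IAC". It adds that IAC may worsen the risks of disease and standard therapy.

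Item (5) Minimizing Risks sends SAEs thought likely to be related for stopping-rule evaluation. Section 6(c) Data and Safety Monitoring sends treatment-related SAEs for biometric review and lists the data evaluated as: "Treatment related toxicities; unanticipated adverse events".

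**The concern.** The capture sentence makes relatedness a condition of entry, yet the scale beneath it has two grades that are useful only if events judged not related are also entered. Staff could follow either reading, and no other section settles the matter.

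The choice matters because the competing explanations are strong. The toxicities named as being of greatest concern include pulmonary infiltrates, GVHD and graft rejection. These overlap with the lung toxicity, infection and GVHD listed as known transplant risks. First infusion falls within 42 days of engraftment in cohort 1 and within 120 days in high-risk cohort 2 patients, so a transplant explanation will often be at hand. The study is open label without a control arm, so an all-cause listing is the simplest way to see the same event recurring across patients.

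If events ascribed to transplant or disease are not entered, some IAC-caused events may be among them. The toxicity rate would then be understated and the count behind the more-than-one rule would be short.

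**Working it through.** **Step 1: is there an all-cause recording rule?** The places where one could appear are these.

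| Place | What it covers |
|---|---|
| f) Study Variables, endpoint and capture sentences | Events assessed as treatment-related |
| f) Study Variables, attribution scale | Five grades, including unlikely and unrelated |
| Schedule of Events | A toxicity assessment at every time point, including screening; what is recorded is not stated |
| Risks to Subjects (5) | SAEs thought likely related |
| 6(c) | Treatment-related toxicities, unanticipated events, treatment-related SAEs |

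None requires recording regardless of attribution. An event that is expected after transplant and judged unrelated fits none of the review categories in the last two rows.

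**Step 2: which events reach stopping-rule evaluation?** Section f) counts possible events. Minimizing Risks forwards SAEs thought likely related, and the scale in section f) uses that degree of likelihood to define its probable grade. A possible event can therefore count under one section and not be forwarded under the other.

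**Step 3: reproduce the stated assurance.** Inputs from section e): n = 10 per cohort, rate 30%, closure at two or more events. With X binomial(10, p):

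P(X ≥ 2) = 1 − (1 − p)^10 − 10p(1 − p)^9

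At p = 0.30 this is 1 − 0.0282 − 0.1211 = 0.851. If tolerance is read as zero events, P(X ≥ 1) = 1 − 0.0282 = 0.972. Both meet the stated 80%.

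**Step 4: allow for incomplete attribution.** Let s be the share of true IAC-caused events that are judged related and so counted. The documents give no value, so s is an assumption shown over a range. The counted rate is 0.30 × s.

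| s | Counted rate | P(X ≥ 2) | P(X ≥ 1) |
|---|---|---|---|
| 1.0 | 0.300 | 85.1% | 97.2% |
| 0.95 | 0.285 | 82.6% | 96.5% |
| 0.9 | 0.270 | 79.8% | 95.7% |
| 0.8 | 0.240 | 73.3% | 93.6% |
| 0.7 | 0.210 | 65.4% | 90.5% |
| 0.5 | 0.150 | 45.6% | 80.3% |

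P(X ≥ 2) equals 80% at a counted rate of 0.271, so s = 0.271/0.30 ≈ 0.90. On the zero-event reading the break-even counted rate is 0.149, so s ≈ 0.50.

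**Step 5: the same point as an upper limit.** With 1 counted event in 10, the one-sided 80% exact upper limit for the counted rate is 27.1%. Dividing by s gives 30.1% for the true rate at s = 0.9 and 33.9% at s = 0.8.

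**The case against.** The sentence says what happens to related events; it does not say that others are excluded. The unlikely and unrelated grades, and a toxicity assessment at screening when nothing can yet be due to IAC, suggest wider recording was intended. Possible events count as related, so an event of uncertain cause should fall on the counted side. In an uncontrolled study this could even inflate the rate. The cohort 2 stop for one steroid-refractory GVHD or graft failure carries no attribution condition. All of this stands. It makes the defect an inconsistency plus a missing rule, not a demonstrated decision to discard events. It does not supply the missing rule, and counting possible events helps only if the event is put on the scale at all.

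A reader might infer that missed events could never be re-judged. The documents do not support that. Two weekly meetings review patients, the DSMB/HROC looks at data after the first 2-3 patients, and CIBMTR forms or the medical record remain as sources. However, none is specified as a step for re-adjudicating AEs.

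A reader might also calculate that if exactly two true events occur and each is missed with probability 20%, 30% or 50%, the rule fails to fire with probability 1 − (1 − q)² = 36%, 51% or 75%. The arithmetic is right, but q is assumed and exactly two events is the case least favourable to this rule. These figures measure misattribution, not the recording gap. An event recorded but graded unrelated would still not count.

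**Conclusion.** The concern holds in a limited form. The capture sentence puts judgement before recording, contradicts its own scale, and is not corrected elsewhere, in a setting where the protocol concedes that the judgement is hard. Following it literally can leave relevant events out of the AE dataset behind the primary endpoint, so toxicity may be understated and a pattern across patients missed.

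The size of the effect is unknown. The illustration shows that the 80% assurance under the more-than-one rule depends on nearly complete attribution: it is lost once roughly one true event in ten goes uncounted. Under a zero-event reading about half would have to be missed. These figures assume a true rate of 30%, independent patients, a common s, and no offsetting events wrongly attributed to IAC. The sample size itself is not in dispute.

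The mismatch between possible events in section f) and likely-related SAEs in Minimizing Risks is a separate contradiction that bears directly on the stopping count.

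**What to change.** Replace the capture sentence in section f). From first IAC infusion to the end of the existing 12-week toxicity window, record and grade all grade 3 or higher AEs, SAEs, deaths, and GVHD, graft-loss or autoimmune events regardless of attribution. Assign the five-level attribution afterwards.

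Report all-cause and related (definite, probable or possible) rates per cohort. Send the all-cause listing to the existing weekly meetings and to the DSMB/HROC, so that attributions can be questioned.

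Reconcile section f) with Minimizing Risks on which attribution grades go to stopping-rule evaluation. The stopping thresholds need not change for this point.

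This makes attribution checkable. It does not by itself raise the probabilities above, because an event still graded unrelated would still not count. The cost is a protocol wording change, a longer AE listing with many transplant-related entries, and more data entry for 20 patients. The documents give no AE workload figures from which to size that.

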This pilot study will determine the tolerance and anti-tumor efficacy of irradiated haploidentical blood mononuclear cells (irradiated allogeneic cells, IAC) in patients with high-risk hematologic malignancies who have undergone autologous or allogeneic hematopoietic stem cell therapy. There will be 2 cohorts:

-Cohort 1 will be composed of patients with high-risk non-Hodgkin lymphoma or multiple myeloma; they will have undergone high dose chemotherapy with *autologous* stem cell rescue but remain at high risk for relapse.

-Cohort 2 will be composed of patients with high-risk hematologic malignancies who have undergone an HLA-matched *allogeneic* hematopoietic stem cell transplant. The IAC will be administered either prophylactically (for those identified to be at high risk at the time of transplant) or after molecular, immunophenotypic or clinical relapse (if the patient is not a candidate for standard donor lymphocyte infusion or alternate standard therapy).

- **Primary Objective**

The primary objective is to determine the toxicity associated with the administration of IAC to patients with high-risk hematologic malignancies.

- **Secondary Objective**

To secondary objective is to determine if there is evidence of disease response associated with IAC. This will be determined by standard disease staging, use of minimal residual disease markers, and/or by clinical analysis by the Hematologic Malignancies Tumor Study Group as directed by disease and disease state.

- **Tertiary Objective**

To determine if treatment with the irradiated cells induces an immune response targeting tumor associated epitopes.

Hypotheses

-An "allogeneic effect" (enhancement of an immune reaction by the presence of a concurrent allogeneic reaction) has been demonstrated in animal studies, is operative in humans and, can be used to enhance anti-tumor responses (1-6).

-Treatment with IAC, as done previously at ██████████ will induce an "allogeneic effect" that results in a clinical anti-tumor response (6,7).

- IAC induce the production of T cells that target tumor associated epitopes (7).

Primary Endpoint(s)

- Determine the toxicities associated with administration of IAC. The anticipated/projected IAC-associated toxicities of greatest concern include:
 - Short-term toxicities: constitutional/systemic adverse events including fevers, hypotension, pulmonary infiltrates;
 - Long-term toxicities: autoimmune effects, graft-versus-host disease (GVHD), graft rejection;

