Registration: Once a potential donor has been identified for respective patient, both the patient / recipient and the relative/ donor will sign consent to participate in the study. Upon signing the consent, donor will undergo protocol mandated screening for eligibility. Once donor's eligibility is confirmed both patient and donors will be registered for the study by OHRS research staff.

Each participant will be given a unique identifier code. No patient will start treatment prior to registration.

All eligible patients will be treated at [REDACTED] and receive standard treatment per Blood & Marrow Transplant Program Policies.

1. Patients in cohort 1 will be treated initially with IAC within 42 days after hematopoietic engraftment (both neutrophils and platelets). Engraftment is

defined by 3 consecutive measurements with absolute neutrophil count > 500/mm³ and platelets > 20,000/mm³ without transfusion.

2. Patients in cohort 2 with *high-risk* disease will be treated initially with IAC within 120 days after hematopoietic engraftment (neutrophils and platelets). Chimerism studies must reveal engraftment of donor CD3+ cells > 80% and there must not be any evidence of > grade I *acute* GVHD or *severe* chronic GVHD, per standard CIBMTR staging.
3. Patients in cohort 2 being treated for *relapsed* disease may receive initial treatment with irradiated allogeneic cells any time after relapse documented. They may receive disease specific therapy prior to the experimental cell therapy, but they must have recovered from the disease-specific therapy prior to the experimental cell therapy.
4. All treated patients who do not have evidence of relapse or progressive disease may be treated q 8-12 weeks for up to 3 treatments with delays up to 8 weeks as clinically indicated.
5. Donor will undergo evaluation at RWJ Blood Services within 7 days of each infusion.
6. Donors meeting eligibility requirements will be harvested by leukapheresis with targeted CD3+ (0.5-3.0 x 10⁸/kg); harvesting will be done according to FACT and AABB guidelines.
7. Donor cells (0.5-3 x 10⁸ CD3+/kg) will be irradiated (25 Gy) and infused no more than 24 hours after harvesting of the cells; in case of ABO incompatibility either RBC depletion will be undertaken or the product will be split to assure infusion of \leq 10 ml ABO incompatible RBC/day.
8. Management of cytopenias, infections, and other complications will conform to standard procedures at the discretion of the physician.

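### Relapsed cohort 2 patients have no GVHD limit at first infusion, and the cohort 2 safeguards credited to the inclusion criteria are not in them

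*Combined protocol and SAP*

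**What the plan says.** Cohort 2 has two routes to treatment. In the opening description, IAC is "administered either prophylactically (for those identified to be at high risk at the time of transplant) or after molecular, immunophenotypic or clinical relapse". The same description restricts the relapse route: "if the patient is not a candidate for standard donor lymphocyte infusion or alternate standard therapy".

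The Treatment Plan gives each route its own rule for first IAC.

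- Item 2 (high-risk disease) sets a window of 120 days after engraftment and requires donor CD3+ cells above 80%. On acute GVHD it says "there must not be any evidence of > grade I". It also bars severe "chronic GVHD, per standard CIBMTR staging".
- Item 3 (relapsed disease) says that patients "may receive initial treatment with irradiated allogeneic cells any time after relapse documented". If they have had disease-specific therapy, "they must have recovered from the disease-specific therapy prior to the experimental cell therapy". It sets no other condition.

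Section f) Study Variables calls steroid-refractory GVHD or graft failure in cohort 2 a major concern and says where the protection lies: "steroid-refractory GVHD OR graft failure (in cohort 2), specific parameters to diminish the likelihood of these events are included in the inclusion criteria". Its two examples are lasting engraftment and high donor chimerism. Section e) Sample Size Justification/Statistical Analysis states the stopping rule: "If there is (1) a steroid refractory GVHD or (2) graft failure in cohort 2, then the study will stop". Section f) repeats that a single episode is enough.

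**The concern.** A reader of section f) would expect to find the protective criteria under Subject Screening - PATIENT. They are not there, and the only GVHD limit in the protocol covers one of the two cohort 2 routes. Followed as written, the plan would allow IAC in a relapsed allograft recipient whose active GVHD would bar a high-risk patient.

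Two things are at stake. The first is patient safety: the Reasonably Foreseeable Risks section names GVHD as a way in which immune activation could show itself after an allograft. The second is the primary result. Toxicity is the primary objective, and one steroid-refractory episode stops the study. If GVHD is present at entry and its stage is not recorded, it will be hard to say later whether IAC caused it, worsened it or had no part in it. The protocol itself admits that attribution may be difficult in these patients.

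**Working it through.** This is a comparison of texts, and no figure in the plan is disputed. The one nearby figure, that 10 patients per cohort give at least an 80% chance that the true unacceptable rate is below 30%, reproduces. With closure at more than one event, P(X ≤ 1 | n = 10, p = 0.30) = 0.7^10 + 10 × 0.3 × 0.7^9 = 0.028 + 0.121 = 0.149, so the confidence is 1 − 0.149 = 85.1%. The point made here does not change it.

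**Step 1: are the safeguards in the inclusion criteria?** The cohort 2 inclusion list consists of disease and risk categories, one of which admits any malignancy relapsed or persistent after allogeneic transplant. The general lines add age, a potential haploidentical donor, fitness for the transplant with consent to it, and language. The fitness line concerns eligibility for the transplant, so it cannot screen for GVHD that arises afterwards. The four patient exclusions are language, transplant donor match, pregnancy and childhood. Criteria on GVHD: 0. On engraftment: 0. On chimerism: 0.

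**Step 2: where are the limits, and for whom?**

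- Item 2, high-risk route: engraftment required; donor CD3+ above 80%; GVHD limits = 2 (acute and chronic).
- Item 3, relapse route: recovery from any disease-specific therapy; GVHD limits = 0.

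**Step 3: could item 2 cover the relapsed patients too?** The cohort 2 inclusion list is headed as patients with high-risk disease, so one might try to read item 2 as cohort-wide. That reading fails. The cohort description separates those at high risk at the time of transplant from those treated after relapse. Item 3's freedom to start at any time after relapse also cannot be squared with item 2's 120-day window. The two items are parallel rules.

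**Step 4: does anything else set a limit?** The Schedule of Events has history, examination and toxicity assessment within 7 days before each infusion. Cases are reviewed weekly, and the monitoring board looks at the data after the first 2-3 patients. These may bring GVHD to notice, but none says what degree of GVHD bars infusion. The condition on donor lymphocyte infusion does not exclude GVHD either; clinically, GVHD may be the reason a patient cannot have donor lymphocytes.

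**Step 5: what triggers a stop?** Steroid-refractory GVHD: 1 episode. Other irreversible treatment-related grade 3 or higher events: more than 1, that is, 2. The sentence in section e) does not require onset after IAC.

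**The case against.** Five objections deserve weight.

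1. *Section f) does not promise a GVHD-grade limit.* A reader might infer that it does and that item 3 breaks the promise. The only examples given are engraftment and donor chimerism. A GVHD limit may have been meant as well, but the text does not say so. What stands is narrower: the parameters are said to be in the inclusion criteria and are not, and separately item 3 has no GVHD limit.

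2. *Irradiation prevents GVHD.* Research Significance says that irradiation assured neither engraftment nor GVHD in the earlier series, and none was seen in its 15 patients. This is the protocol's best argument for a low direct risk. However, that series had renal cell carcinoma, melanoma or AML and is not described as post-allograft. Section f) and Reasonably Foreseeable Risks still name GVHD from immune activation as a risk in allograft recipients. The argument reassures only in part.

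3. *The difference between routes may be deliberate.* Relapsed patients have few alternatives, and some may be on this route because GVHD rules out donor lymphocytes. Nothing in the documents shows that item 2's threshold is the right one in relapse. This is a real cost. If the omission is intended, though, the protocol gives no reason for it.

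4. *The stopping rule may cover only GVHD triggered by IAC.* The single-episode sentence in section f) refers back to events that IAC might trigger; the shorter sentence in section e) has no such link. One should therefore not conclude that the rule plainly counts pre-existing GVHD. The wording is ambiguous, and without a baseline stage it would be hard to apply under either reading.

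5. *An entry limit does not cure the stopping problem.* This is correct. Grade I acute and non-severe chronic GVHD would still be admitted on both routes and could become steroid-refractory.

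**Conclusion.** The point holds in this form. The cohort 2 safeguards that section f) places in the inclusion criteria are absent from them, and the relapse route has no GVHD limit at first IAC. The gap is 2 GVHD limits against 0, set beside a stop at 1 episode. This rests on reading items 2 and 3 as separate rules and on there being no screening rule outside the text; unstated programme policy or physician judgement may already keep such patients out.

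Three stronger conclusions are not supported. The documents do not show that relapsed patients need item 2's engraftment or donor CD3+ limits; for those, the only fault is the description in section f). They give no rate of GVHD in relapsed patients, so neither the harm nor the chance of early termination can be sized. And closing the gap would reduce, not remove, the chance that GVHD present at entry stops the study. The change is still worth making, because it is cheap, bears on a risk the protocol ranks as major, and makes the primary toxicity result easier to interpret.

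**What to change.** 1. Add item 2's GVHD limit (no acute GVHD above grade I and no severe chronic GVHD at first IAC, by CIBMTR staging) to Treatment Plan item 3 and to the cohort 2 inclusion list.
2. Record GVHD stage before first IAC for every cohort 2 patient, at the history and examination already scheduled. GVHD present at entry can then be told apart from new or worsened GVHD, both in the primary toxicity assessment and when the single-episode stopping rule is applied.
3. Correct section f) to say that the engraftment and donor CD3+ limits are in Treatment Plan item 2 and apply to the high-risk stratum only. Do not add a chimerism threshold for relapsed patients.

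The cost is a few wording changes and one recorded stage per cohort 2 patient, with no new test or visit. The downside is that a few relapsed patients would no longer qualify, possibly including some who cannot have donor lymphocytes because of GVHD.
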